### Area-level outcomes

For the area-level outcomes, our main analysis will examine 1,635 treated LSOAs, which would give a minimum detectable difference of 25% of an SD (Table 1).

# 12. Sampling procedure

For our impact and economic evaluations, our intervention group will include all selective licensing schemes operating in England after 2012, as identified by Freedom of Information (FOI) requests to all English local authorities. Comparison areas will be identified through matching (see Section 18).

The qualitative sample for work package 2 is designed to include a diverse range of stakeholders and tenants. We agreed a lower limit of 48 semi-structured interviews in four study sites: 12 per site (2 implementers, 2 from community organisations representing tenants, 3 PRS property managers/landlords, 5 tenants). If needed, to help ensure diversity in the sample, we have an upper limit of 78 semi-structured interviews (along with the two workshops): 18 per site (4 implementers, 2 from community organisations representing tenants, 4 PRS property managers/landlords, 8 tenants). We will also hold two workshops (n=10 participants each). The first workshop will include national and regional stakeholders. The second workshop will include local stakeholders including, but not limited to, stakeholders working in our four study sites.

# 13. Participant selection

For the qualitative analyses, we will recruit stakeholders (national organisations, local implementers, PRS property managers/landlords, community organisations representing tenants, tenants). We will use our existing network of contacts and recruit locally through snowballing and advertising as required. See section 18 for further details. We will use interpreters if required (see Section 28 for further details).

The impact evaluation (WP1,3) is based on secondary data analysis and does not involve recruitment of participants.

# 14. Variables and data sources

### 14a. Variables

### Individual-Level Outcomes

We have chosen outcome measures based on previous research on housing interventions and policy aims. Poor quality homes and unsafe neighbourhoods present both mental and physical risks. Our primary outcome will be **high levels of anxiety self-reported in the Annual Population Survey (APS)**, measured as people reporting a score of more than 6 in response to the question "Overall, how anxious did you feel yesterday?", where 0 is 'not at all anxious' and 10 is 'completely anxious'. A threshold of more than 6 on the 11-point scale has been identified by the ONS as a measure of high anxiety levels.

Our secondary outcomes will be the three other measures of subjective wellbeing (happiness, life satisfaction and feeling worthwhile) included in the APS. We will also examine the general self-reported health measure collected by the APS as an indicator of health that includes both mental

and physical health. To investigate potential unintended consequences of SL, we will also examine the APS respondent's number of years at the current address as an indicator of residential stability.

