We will explore spillover effects by repeating the difference-in-differences analysis with matching for (1) individuals who do not live in private rented sector housing and (2) for individuals who live in LSOAs that are first-order neighbours of SL areas. For (1) we will compare individuals who do not live in private rented sector housing in SL areas to individuals who do not live in private rented sector housing in the control areas that we have matched to treatment areas for the main analysis. For (2) we will treat the first-order neighbours of treated LSOAs as if they are intervention LSOAs and match

them to comparable LSOAs that are neither SL areas nor SL area neighbours. We will report the average effects over the first five years after the intervention (0 to 5 years) as the main result. We will report this together with an event time plot showing all available years before and after the interventions. In addition, we will report delayed effects and longer-term effects as secondary results.

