# 11. Sample size

#### *Individual-level outcomes*

For the individual-level outcome measures, we estimate that the APS includes about 1,000 respondents per year who live in private rented accommodation in LSOAs covered by SL schemes, so over our 2012 to 2019 sample period we expect to observe around 8,000 individuals in the intervention group (5.5% of the England population live in the schemes included in the study). The number of APS participants in the matched comparison LSOAs will be approximately 3000 per year if we match 3 control LSOAs to every intervention LSOA.

As the power calculation for our staggered treatment timing difference-in-differences design with repeated cross-section data would be very complicated, we ran a power calculation for the canonical difference-in-difference design with one pre- and one post-intervention observation to get a broad idea of the statistical power of our analysis. The power calculations are based on a bootstrapping algorithm with 1,000 repetitions with 95% significance level and a 3:1 ratio between control to intervention units. The outcome variable was designed as normal-distributed and z-standardised in an artificial dataset. With just 1,000 respondents – the potential annual number of respondents in treated areas – the minimum detectable difference would be 30% of an SD (Table 1).

Table 1 Power calculations based on bootstrapping algorithm with 1,000 repetitions for a DiD design with 95% significance level, one pre- and one post-intervention observation, and 3:1 ratio between control to intervention units (Burlig et al. 2020) [36]. The outcome variable was designed as normal-distributed and z-standardised. Cells shaded in grey indicate power calculations at or above 80%. A unit can correspond to either a respondent or a LSOA area depending on the context. N corresponds to the number of treated units.

| N    | 10%SD | 15%SD | 20%SD | 25%SD | 30%SD |
|------|-------|-------|-------|-------|-------|
| 1000 | 0.167 | 0.291 | 0.523 | 0.694 | 0.837 |
| 1500 | 0.195 | 0.440 | 0.637 | 0.864 | 0.953 |
| 2000 | 0.272 | 0.540 | 0.800 | 0.934 | 0.989 |
| 2500 | 0.333 | 0.659 | 0.884 | 0.972 | 0.997 |
| 3000 | 0.379 | 0.706 | 0.923 | 0.987 | 0.998 |
| 3500 | 0.423 | 0.787 | 0.958 | 0.989 | 1.000 |
| 4000 | 0.515 | 0.833 | 0.979 | 0.997 | 1.000 |
| 4500 | 0.568 | 0.876 | 0.988 | 0.999 | 1.000 |
| 5000 | 0.593 | 0.894 | 0.993 | 0.998 | 1.000 |
| 5500 | 0.652 | 0.930 | 0.993 | 1.000 | 1.000 |

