We therefore use as our controls individuals who live in private rented housing in LSOAs without SL that are not direct neighbours of LSOAs with SL. From among these controls, we choose those individuals who live in LSOAs that we have matched to the treated LSOAs using characteristics of the LSOAs such as proportion of individuals who are under 16, proportion of individuals who are non-white and proportion of households classed as overcrowded.

Our individual-level outcome measures come from repeated cross-sectional data, so each year different individuals are being observed in each LSOA. The starting point for our analysis is the canonical two-way fixed effects regression specification:

$$Y_{iat} = \alpha_a + \varphi_t + \beta D_{at} + \varepsilon_{iat}$$

 Y_{iat} indicates one of our outcome measures for individual *i* in LSOA *a* in year *t*. α_a is an LSOA effect, which accounts for time-invariant differences between the LSOAs, and φ_t is a year effect, which accounts for changes over time happening in all LSOAs. D_{at} takes the value 1 if LSOA *a* is subject to an SL scheme in year *t* and 0 otherwise. β is the treatment effect, i.e. it captures the impact of the SL scheme. In the special case of only two years *t* (before and after the intervention) the ordinary least squares (OLS) estimate $\hat{\beta}$ is equivalent to the difference-in-differences estimate $\hat{\gamma}$:

$$\hat{\gamma} = \left(\bar{Y}_{SL,AFTER} - \bar{Y}_{SL,BEFORE}\right) - \left(\bar{Y}_{COMPARATOR,AFTER} - \bar{Y}_{COMPARATOR,BEFORE}\right)$$

 $\overline{Y}_{SL,AFTER}$ is the mean of the outcome measure in the LSOAs with an SL scheme after implementation of the SL scheme and $\overline{Y}_{SL,BEFORE}$ is the mean before implementation. $\overline{Y}_{COMPARATOR,AFTER}$ is the mean of the outcome measure in the matched comparator LSOAs in the year after SL was implemented in the SL areas and $\overline{Y}_{COMPARATOR,BEFORE}$ is the mean in the year before implementation. Unfortunately, this intuitive causal interpretation of the parameter estimate $\hat{\beta}$ is unlikely to apply in the more general case of more than two years *t* and the intervention being rolled out over several years. As the implementation of SL schemes is at the discretion of local authorities, they have been rolled out at different times over many years.

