13. Participant selection

The impact evaluation (WP1,3) is based on secondary data analysis and does not involve recruitment of participants.

14. Variables and data sources

14a. Variables

Individual-Level Outcomes

We have chosen outcome measures based on previous research on housing interventions and policy aims. Poor quality homes and unsafe neighbourhoods present both mental and physical risks. Our primary outcome will be **high levels of anxiety self-reported in the Annual Population Survey (APS)**, measured as people reporting a score of more than 6 in response to the question "Overall, how anxious did you feel yesterday?", where 0 is `not at all anxious' and 10 is `completely anxious'. A threshold of more than 6 on the 11-point scale has been identified by the ONS as a measure of high anxiety levels.

Our secondary outcomes will be the **three other measures of subjective wellbeing (happiness, life satisfaction and feeling worthwhile)** included in the APS. We will also examine **the general self-reported health measure collected by the APS** as an indicator of health that includes both mental and physical health. To investigate potential unintended consequences of SL, we will also examine the **APS respondent's number of years at the current address** as an indicator of residential stability.

Area-Level Outcomes

Our primary area-level outcome will be the **Small Area Mental Health Index (SAMHI)** and its individual domain scores. The index is available for LSOAs on an annual basis [13]. It combines the following measures of mental healthcare use into a single index: mental health-related hospital admissions, antidepressant treatment days per population, proportion of the population diagnosed with depression, proportion of population in receipt of mental health-related benefits.

We will complement the analysis with an exploration of physical health outcomes. Since the treated areas are relatively small, most physical health outcomes are not available at the spatial granularity needed for the analysis. However, we can use **1. All-cause emergency hospital admissions** as an

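### Years at the current address is a lagged measure of displacement, so a null in the 0-to-5-year result should not be read as no displacement; pre-specify a recent-mover indicator beside it

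*Protocol*

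**What the plan says.** Protocol 14a (Individual-Level Outcomes) scores the outcome as "number of years at the current address as an indicator of residential stability" and gives its purpose as the search for possible unintended effects of licensing. SAP 14a repeats the same item, "number of years at the current address". Protocol section 21 lists residential stability as an individual-level secondary outcome.

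On the data, SAP 9a states: "Our individual-level outcome measures come from repeated cross-sectional data, so each year different individuals are being observed in each LSOA". People who leave are therefore not followed. On scale, Protocol section 11 says that "over our 2012 to 2019 sample period we expect to observe around 8,000 individuals in the intervention group".

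On reporting, Protocol 9a (and SAP 9a in the same terms) says: "We will report the average effects over the first five years after the intervention (0 to 5 years) as the main result". This sentence sits in the spillover paragraph, but the documents give no other headline window, so I read it as the main result for the individual-level outcomes generally. It is accompanied by an "event time plot showing all available years before and after the interventions", and the plan adds: "In addition, we will report delayed effects and longer-term effects as secondary results".

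The plan specifies no recent-mover indicator, no cap at the licensing date and no allowance for lag. The Variable transformations text in section 18 permits outcomes to be dichotomised, but names neither this outcome nor a cut-point. The documents give no mean, SD or move rate for the item, and do not describe its response categories.

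**The concern.** Years at the current address is a stock. A tenant interviewed in 2016 under a 2015 scheme after nine years in the home scores 9, and at least seven of those years came before the scheme. Someone who has just replaced a displaced tenant scores close to zero. If licensing raises the move rate, the mean falls only as residents from before licensing are replaced, while the main result averages the period in which that replacement is incomplete.

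Displacement is central to the theory of change in Protocol 7c: the area-improvement and stop-renting hypotheses both predict that tenants lose their homes. This is the individual-level quantitative outcome aimed at it among private tenants. A small or null 0-to-5-year estimate could be taken as reassurance when the measure has not had time to respond.

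**Working it through.** The plan states no figure for this outcome, so there is none to reproduce. The check asks how much of the long-run change each measure shows in the 0-to-5-year average.

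**Inputs from the documents.** Treated LSOAs by first year, summed from Table S1: 2012, 168; 2013, 10; 2014, 128; 2015, 757; 2016, 77; 2017, 72; 2018, 381; 2019, 42; total 1,635. With observation to 2019, the numbers seen at event years 0 to 5 are 1,635, 1,593, 1,212, 1,140, 1,063 and 306 (sum 6,949). Only 306 reach year 5, because the 2015 cohort stops at year 4.

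**Assumptions, not in the documents.** Yearly move rate h0 of 0.15, 0.25 or 0.40 before licensing, constant over the stay; a permanent 20% rise to h1 = 1.2 × h0 at the start; start dates and interviews spread evenly over the calendar year; LSOA counts standing in for respondent counts.

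**Mean years.** At elapsed time s the mean is (1 − exp(−h1·s))/h1 + exp(−h1·s)/h0. The share of the long-run change visible is 1 − exp(−h1·s), averaged over the spread of s within each event year.

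Example, h0 = 0.25 and h1 = 0.30:
- Long-run change: 1/0.30 − 1/0.25 = −0.67 years.
- Share visible at event years 0 to 5: 4.6%, 25.4%, 44.7%, 59.0%, 69.7%, 77.5%.
- Cohort-weighted: (1,635×0.046 + 1,593×0.254 + 1,212×0.447 + 1,140×0.590 + 1,063×0.697 + 306×0.775)/6,949 = 38%, or about −0.26 years.
- Equal weights: 280.9%/6 = 47%.

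**12-month indicator, same example.** The proportion moves from 1 − exp(−0.25) = 22.1% to 1 − exp(−0.30) = 25.9%, a rise of 3.8 points. Shares visible are 17%, 83%, then 100% from year 2. Cohort-weighted this is 77%, and with equal weights 83%.

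| Move rate | Mean years, cohort / equal | Indicator, cohort / equal |
|---|---|---|
| 0.15 | 27% / 34% | 77% / 83% |
| 0.25 | 38% / 47% | 77% / 83% |
| 0.40 | 50% / 59% | 77% / 84% |

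**Outside that range** (cohort-weighted, mean years). Mean stays of 1 to 2 years show 70% to 56%; a mean stay of 15 years shows 14%. If the effect starts only at year 3, as Protocol 7b reports for the London study's impacts generally, the equal-weighted share (elapsed time taken as the event year) is 19%, 12% and 7% for mean stays of 2, 4 and 8 years.

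**How much of the score predates licensing.** On the same simple timing, averaged over event years 0 to 5, the share of mean years accrued before the start is 38% at a mean stay of 2 years, 49% at 3, 57% at 4 and 74% at 8.

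**Detectability.** The shares have different endpoints, so I also put both effects in SD units: for mean years the change divided by the SD of elapsed stay (1/h0 under a single rate), for the indicator the change divided by √(p(1−p)), where p is the baseline proportion.
- One common move rate, cohort weights (mean years v indicator): 0.045 v 0.056 at 0.15; 0.064 v 0.070 at 0.25; 0.084 v 0.084 at 0.40. Equal weights: 0.056 v 0.061; 0.078 v 0.076; 0.099 v 0.091.
- Short and long stayers mixed, 20% rise in both groups, cohort weights. Half with mean 2 and half with mean 10 years: 0.031 v 0.068 (ratio 2.2). 70% with mean 2 and 30% with mean 10: 0.033 v 0.076 (2.3). Half with mean 1.5 and half with mean 6: 0.045 v 0.076 (1.7). 70% with mean 1 and 30% with mean 15: 0.018 v 0.078 (4.4).
- Rise confined to the first year, h0 = 0.25, one common rate: the indicator is zero from event year 3, while mean years keeps some effect through year 5. Weighted averages are 0.024 for mean years and 0.020 for the indicator.

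**The case against.** **Bias.** A reader might infer that the outcome is biased towards no harm. The documents do not support that. The difference-in-differences estimate targets the effect on mean years within the window, and the plan calls the item only an indicator of stability. A short-run effect smaller than the long-run one is a lag. What stands is that a null is easily misread.

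**Fixed attenuation.** It is also tempting to say that a quarter to a half of a rise in displacement will show, or that the score is mostly time before licensing. Both depend on a tenure distribution the documents do not give, and the second fails at mean stays of about three years or less. The fraction is of the long-run change in mean years, not of displacement itself. The plan allows different aggregation schemes, so cohort weights are not fixed either. If licensing displaced long stayers preferentially, mean years would respond faster.

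**Power.** With one common move rate the two measures are about equally detectable, and mean years is sometimes better. That is correct, but it depends on homogeneous stays: in the mixtures of short and long stayers above, the indicator has 1.7 to 4.4 times the standardised signal.

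**One-off exits.** A burst of moves around licensing, which the stop-renting hypothesis could produce, persists in mean years and disappears from a 12-month indicator. This stands, and it is why mean years should not be dropped.

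**Existing safeguards.** The event-time plot, the longer-term results, the area-level turnover index and the tenant interviews all soften the problem. But the main average is unchanged, the turnover index is not described as restricted to private tenants, and the permission to dichotomise leaves the cut-point open.

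**Conclusion.** The concern holds as one of lag. Residential stability is scored as a duration that includes time before licensing, and nothing in the plan adjusts the 0-to-5-year result for this. Under a constant move rate of 0.15 to 0.40 and a permanent 20% rise, about 27% to 50% of the long-run change in mean years is visible with cohort weights and 34% to 59% with equal weights, against about 77% to 83% for a 12-month mover indicator, whose share hardly depends on the assumed rate. The direction holds at every tenure tested; the size is conditional on figures the documents do not supply. This is a secondary outcome, so the consequence is a risk of false reassurance about displacement and does not touch the primary analysis.

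**What to change.** In the SAP, pre-specify from the same APS item an indicator of being at the current address for less than 12 months, or the shortest recorded band if the item is banded. Make it the secondary outcome for displacement, analysed with the same difference-in-differences model. Check first that the item allows this cut, since the documents do not show its categories.

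Keep mean years at address as a reported companion outcome with its event-time plot. State that it is a lagged measure and that a null in the 0-to-5-year average is not evidence of no displacement.

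The cost is SAP wording, one recoded variable and one more test in the false-discovery-rate family. The binary item drops information on long stays, can be slightly less precise if stays are homogeneous and short, and loses a one-off burst of moves in later event years. The retained companion outcome covers that last loss.

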#### *Area-Level Outcomes*

Our primary area-level outcome will be the **Small Area Mental Health Index (SAMHI)** and its individual domain scores. The index is available for LSOAs on an annual basis [37]. It combines the following measures of mental healthcare use into a single index: mental health-related hospital admissions, antidepressant treatment days per population, proportion of the population diagnosed with depression, proportion of population in receipt of mental health-related benefits.

We will complement the analysis with an exploration of physical health outcomes. Since the treated areas are relatively small, most physical health outcomes are not available at the spatial granularity needed for the analysis. However, we can use 1. All-cause emergency hospital admissions as an indicator of the population's overall health. The choice of emergency admissions are in line with the literature on preventable hospitalisation [38,39]. Similar measures have been used to evaluate public health and social care interventions, including housing [16,40]. Hospital admissions data are available for LSOAs on an annual basis. This indicator is equivalent and a counterpart to the mental health-related hospital admissions element of the SAMHI and can be extracted from the Hospital Episode Statistics data (NHS Digital), which the University of Liverpool has access to. In addition, we will examine 2) Cardiovascular emergency admission in 65+yr, 3) Respiratory emergency admission in 65+yr, 4) Emergency admission injuries falls/burns in 65+yr (any place of occurrence), 5) Asthma emergency admission, a) All ages, b) 0-14yr, c) 65+yr, 6) All-cause A&E attendance, a) All ages, b) **65+yr**. There is evidence for these outcomes showing associations with the home environment [41– 43]. Older people are particularly vulnerable to poor quality housing. By the same token, we will study emergency asthma admissions among 0-14-year-olds. Rodgers et al. 2018 studied emergency admission injuries falls/burns in 65+yr occurring in the home. This level of detail, i.e. place of occurrence, is not available in the data available to us and we will study this is as 'any place of occurrence'.

**Incidence of police-recorded ASB**: High levels of ASB is one of the most common reasons for local authorities to implement SL [9] . These data are available for LSOAs on a monthly basis [44].

**Population turnover index**: An increase in population turnover might indicate unintended consequences of SL. The population turnover index is based on a combination of electoral roll and consumer data [45].

**Tenants' rent (£):** We have gained access to Zoopla Property Data through the Urban Big Data Centre at the University of Glasgow [46]. Zoopla is one of the largest online property advertising companies. The Zoopla data affords a much higher level of granularity than government data on property rents, which are only available at regional level. The data are based on daily extractions, so they reflect day-to-day advertising rather than stock value at any given moment.

University of Glasgow (pers. comm., 17 Jun 2024), the owner of the Zoopla rent data, does not recommend combining data from before and after they changed the way they scrape the data from the Zoopla website in 2019. The first full year of data is 2012. Therefore, for this outcome measure we will study only 2012-2018 instead of 2011-2019.

Listings were selected that qualified on the following criteria (Figure S2): Generation 1 Zoopla data, rentals, residential 2-bedroom properties, non-missing last marketed data 2012-2018, England, first listing per property per year.

We will use the mean rent for a 2-bedroom home with the bottom and top centiles removed to address outlier issues. We will also study the same for 2-bedroom flats ('flat' or 'block of flats') as the most commonly occurring property type.

